**6.2. Secondary Efficacy Analyses****6.2.1. Endpoint / Variables**

Secondary Efficacy Endpoints are the following items:

- MAS scores in the elbow, finger, thumb and wrist flexors.

**CONFIDENTIAL**

207660

- Change from baseline in MAS scores
- Responder rate of MAS in the elbow, finger, thumb and wrist flexors.
- DAS score (Main Assessment Parameter)
- Change from baseline in DAS score (Main Assessment Parameter)

**6.2.2. Summary Measure**

Summary Measures are as below.

- The differences in the responder rate of MAS scores
- The differences in the least square means of changes from baseline in MAS scores
- The differences in the least square means of changes from baseline in DAS scores

**6.2.3. Population of Interest**

The secondary efficacy analyses will be based on the Intent-To-Treat 1 population, unless otherwise specified.

The secondary efficacy analyses will be performed for only double blind phase. All efficacy analyses for open -label phase and other endpoints for double blind phase will be done as exploratory.

Unless specified otherwise, the data up to Week 12 of treatment will be summarized during the double-blind period. This is because this study allows to re-treat. In other words, after 12 weeks, only participants who have a smaller MAS score would remain and the difference of the change from baseline in MAS between 240 units and 400 units would be attenuated. Therefore, the data up to Week 12 of initial treatment will be analysed as secondary statistical analyses. This is the case for exploratory analyses for open label period (i.e. the data up to week 12 of re-treatment will be summarized). Listing will include the data after week 12 of treatment/re-treatment.

**6.2.4. Strategy for Intercurrent (Post-Randomization) Events**

Intercurrent event: early withdrawal from study.

Strategy for dichotomous data: the participant will be regarded as a non-responder.

Strategy for continuous data: the missing data will be removed from the analyses.

**6.2.5. Statistical Analyses / Methods**

Details of the planned displays are provided in [Appendix 12: List of Data Displays](#) and will be based on GSK data standards and statistical principles.

Unless otherwise specified, endpoints / variables defined in Section [6.2.1](#) will be summarised using descriptive statistics, graphically presented and listed.

CONFIDENTIAL

207660

**6.2.5.1. Statistical Methodology Specification**

Secondary Efficacy Analysis
Endpoint / Variables

 
Change from baseline in MAS and DAS scores
 

Model Specification

 
The endpoint will be analyzed using a mixed model for repeated measures (MMRM)
 
Terms fitted in the MMRM will include the items below as fixed and categorical effects. 
 
Treatment
 
Visit
 
Treatment-by-visit interaction
 
Baseline value
 
Baseline-by-visit interaction
 
 
 
An unstructured variance structure will be used to model the within-participant errors, shared across treatments.
 
The empirical sandwich estimator will be used to estimate the standard errors.
 

Model Checking & Diagnostics

 
If the model will not converge with unstructured variance, AR(1) variance structure can be used.
 

Model Results Presentation

 
Adjusted means (least square means) and corresponding standard errors of means will be presented for each treatment by visit, together with estimated treatment differences (400 units – 240 units) and the corresponding 95% CI.
 

Data included in Model

 
The dataset including only data until week 12 after the first treatment will be used.
 

Endpoint / Variables

 
Responder Rate of MAS score
 

Model Specification

 
See primary endpoint section.
 

Data Convention

 
See primary endpoint section.
 

Supportive Statistical Analyses

 
See supportive statistical analyses for primary efficacy analyses section.
 

**6.3. Exploratory Efficacy Analyses****6.3.1. Modified Ashworth Scale (MAS)**

These analyses will be based on ITT 2, 3 and 4 populations.

**CONFIDENTIAL**

207660

Values and changes from baseline in MAS scores in finger, thumb, wrist, elbow, pronation of the forearm and shoulder flexors will be summarised using descriptive statistics, graphically presented and listed by visit and treatment cycle. Data up to Week 12 in each treatment cycle will be used for summary tables and Figures, whereas all data will be listed.

**6.3.2. Numeric Rating Scale (NRS) for pain**

These analyses will be based on ITT 1, 2, 3 and 4 populations.

Values and changes from baseline in NRS for pain will be summarised using descriptive statistics, graphically presented and listed by visit and treatment cycle.

**6.3.3. Disability Assessment Scale (DAS)**

These analyses will be based on ITT 1, 2, 3 and 4 populations.

Values and changes from baseline in all items of DAS will be summarised using descriptive statistics, graphically presented and listed by visit and treatment cycle.

**6.3.4. Clinical Global Impression of Change (CGI) of functional disability**

These analyses will be based on ITT 1, 2, 3 and 4 populations.

Values of the variables below will be summarised using descriptive statistics, graphically presented and listed by visit and treatment cycle.

CGI of functional disability by an investigator

CGI of functional disability by a patient

**6.3.5. Patient-Reported Benefit of Injection**

These analyses will be based on ITT 1, 2, 3 and 4 populations.

The number and percentage of patient-reported benefit of injection will be presented and listed by visit and treatment cycle.

**6.3.6. Time to Patient-Reported Onset of Spasticity Symptom Relief**

These analyses will be based on ITT 1, 2, 3 and 4 populations.

Time to event data will be summarized using the descriptive statistics below and listed.

- The number of events and censored cases.
- Median survival time with the associated 95% CI.
- 25% and 75% survival time.

**CONFIDENTIAL**

207660

Survival analyses will be conducted using a Kaplan-Meier method. To graphically compare the survival functions between 400 units and 240 units, the analysis will be conducted based on ITT 1 population whereas the analyses will be based on ITT 2, 3 and 4 populations to assess the survival time by treatment cycle. Participants who are withdrawn from this study before Visit 2 are censored at the withdrawal date. All other participants who do not experience the event and is not withdrawn from study are censored at the Visit 2.

Survival function estimates will be summarized (survival probabilities and the number of participants at risk per time to event, and median in survival time) based on Kaplan Meier method. Kaplan Meier plots will be presented.

**6.3.7. Time to Qualification for Retreatment**

These analyses will be based on ITT 1, 2, 3 and 4 populations.

The number and percentage of event of interest will be presented by visit. Time to event data will be summarized using the descriptive statistics below and listed.

- The number of events and censored cases.
- Median survival time with the associated 95% CI.
- 25% and 75% survival time.

Survival analyses will be conducted using a Kaplan-Meier method. To graphically compare the survival functions between 400 units and 240 units, the analysis will be conducted based on ITT 1 population whereas the analyses will be based on ITT 2, 3 and 4 populations to assess the survival time by treatment cycle. Participants who are withdrawn from this study before the event are censored at the withdrawal date. All other participants who do not experience the event and is not withdrawn from study are censored at the Last Observed Visit at the interim analyses or the final analyses.

Survival function estimates will be summarized (survival probabilities and the number of participants at risk per time to event, and median in survival time) based on Kaplan Meier method. Kaplan Meier plots will be presented.

Note that the retreatment is not allowed within 83 days from the previous treatment. Therefore, this event will not occur before 83 days later after the treatment/re-treatment.

**7. SAFETY ANALYSES**

The safety analyses will be based on the Safety 1, 2, 3 and 4 populations, unless otherwise specified.

**7.1. Adverse Events Analyses**

Adverse events analyses including the analysis of adverse events (AEs), Serious (SAEs) and other significant AEs will be based on GSK Core Data Standards. The details of the planned displays are provided in [Appendix 12: List of Data Displays](#).

**CONFIDENTIAL**

207660

Adverse events that occurred in the overall study period, blinded period and open-label period will be summarized for each treatment group. The treatment group is based on dose actually given in blind period. For the blinded period, 2 patterns of analyses on adverse events will be performed, one is on adverse events that occurred between the initial dose and the first dose in the open-label period (or at the completion of study if no dose is given in the open-label period or at the study withdrawal), and another one is on adverse events that occurred within 84 days from the initial dose.

Overall study period (Treatment Emergent AEs)

Blind phase

1. AEs occurred between the initial dose and the first dose in the open-label period (or at the completion of study if no dose is given in the open-label period or at the study withdrawal)
2. AEs occurred within 84 days from the initial dose

Open-label phase

1. AEs occurred during 2nd treatment cycle.
2. AEs occurred during 3rd treatment cycle.
3. AEs occurred during 4th treatment cycle.

The number and percentages of participants who experience at least one AE will be presented for each category of AE listed as below by treatment group.

- All Treatment Emergent AEs (by SOC and PT, by SOC, PT and Maximum Intensity)
- Common AEs ( $\geq 3\%$ ) (by overall frequency)
- Drug Related AEs (by SOC and PT, by SOC, PT and Maximum Intensity)
- Non-Fatal Serious AEs
- Drug Related Non-Fatal Serious AEs
- AEs Leading to Permanent Discontinuation of Study Treatment or Withdrawal from Study (by SOC and PT)
- Most Common Serious Drug Related AEs (by overall frequency)
- Most Common Non-Serious Drug Related AEs (by overall frequency)
- Common ( $\geq 5\%$ ) Non-Serious AEs (by SOC and PT)
  - Number of Participant and Occurrences will be presented.

“Common ( $\geq 3\%$ ) AEs” is defined as the percentage of AEs is more than and equal to 3% in either treatment group.

In addition, the items below will be listed.

- All AEs
- Participant Numbers for Individual AEs
- Fatal Serious AEs
- Non-Fatal Serious AEs
- Reasons for Considering as a Serious AE

**CONFIDENTIAL**

207660

- AEs Leading Withdrawal from Study/ Permanent Discontinuation of Study Treatment
- Relationship between AE SOC, PT and Verbatim Text.

**7.2. Adverse Events of Special Interest Analyses**

Adverse Events of Special Interest are defined as below.

- Convulsions and Seizures
- Respiratory Adverse Events
- Possible Distant Spread of Toxin

The number and percentage of AESI will be presented by treatment cycle and treatment group. The details of how to identify are described in the [Appendix 13](#).

**7.3. Clinical Laboratory Analyses**

Laboratory evaluations including the analyses of Chemistry laboratory tests, Hematology laboratory tests, Urinalysis, and liver function tests will be based on GSK Core Data Standards. The details of the planned displays are in [Appendix 12: List of Data Displays](#).

These data at Screening Visit, in Blind Phase and at Final Visit will be summarized by visit. Data at all visits will be listed.

Values and change from baseline in Chemistry Laboratory tests and Hematology laboratory tests will be summarized by treatment group and visit.

Worst case results relative to normal range from baseline will be presented for Chemistry, Hematology and Urinalysis.

Shifts from baseline relative to normal range will be summarized by treatment group and visit for Chemistry and Hematology values.

Scatter plot of Chemistry and Hematology at Week 12 versus baseline in Blind Phase will be presented.

The outputs regarding liver events will not be presented unless at least one liver event is observed. See the details in the [Appendix 12](#).

**7.4. Other Safety Analyses**

The analyses of non-laboratory safety test results including ECGs and vital signs will be based on GSK Core Data Standards, unless otherwise specified. The details of the planned displays are presented in [Appendix 12: List of Data Displays](#).

These above data at Screening Visit, in Blind Phase and at Final Visit will be summarized by visit. Data at all visits will be listed.

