### 2.2. Study Objective(s) and Endpoint(s)

Objectives	Endpoints
Primary Objectives	Primary Endpoints

 
To evaluate the efficacy of the injections of 400 units of the product at Week 6 (finger/ wrist flexors: 240 units, elbow flexors: 160 units), comparing to that of 240 units (finger/ wrist flexors: 240 units, elbow flexors: placebo).
 
	
 
The responder rate: The rate of the participants that Modified Ashworth Scale (MAS) score was reduced at least 1 from baseline in the elbow flexors.
 

Secondary Objectives	Secondary Endpoints

 
To evaluate the efficacy of 400 units of the product, comparing to 240 units of the product
 
	
 
The responder rate of MAS score from baseline in the finger, thumb and wrist flexors
 
Changes in MAS score from baseline in the finger, thumb, wrist and elbow flexors
 
Changes in Disability Assessment Scale (DAS) from baseline
 

	
 
Adverse events
 
Physical examinations
 
Clinical laboratory tests (haematology, blood biochemistry, urinalysis)
 

 
To evaluate the safety and tolerability of the product of 400 units, comparing to 240 units of the product/ To evaluate the safety
 
	

Objectives	Endpoints
and tolerability of 400 units of the product	
 
Vital signs (heart rate, blood pressure, body temperature)
 

Exploratory Objectives	Exploratory Endpoints

 
To evaluate the efficacy of 400 units of the product
 
	
 
Changes in MAS score from baseline in finger, thumb, wrist, elbow, pronation of the forearm and shoulder flexors
 

 
To evaluate the other efficacy of the product of 400 units, comparing to 240 units of the product/ To evaluate the other efficacy of 400 units of the product
 
	
 
Changes in Numeric Rating Scale (NRS) for pain from baseline
 

	
 
Changes in other items of DAS from baseline
 

	
 
Clinical Global Impression of Change (CGI) of functional disability by an investigator
 

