## **8.3. Clinical Laboratory Analyses**

Laboratory evaluations including the analyses of Chemistry laboratory tests, Hematology laboratory tests, Urinalysis, and liver function tests will be based on GSK Core Data Standards. The details of the planned displays are in [Appendix 12](#): List of Data Displays.

These data at Screening Visit, in Blind Phase and at Final Visit will be summarized by visit. Data at all visits for participants with any value outside normal range will be listed.

Values and change from baseline in Chemistry Laboratory tests and Hematology laboratory tests will be summarized by treatment group and visit.

Worst case results relative to normal range from baseline will be presented for Chemistry, Hematology and Urinalysis. Worst case urinalysis results relative to baseline for protein (category: NEG, TRA, 1+, 2+, 3+, 4+) and occult blood (category: NEG, TRA, 1+, 2+, 3+) urinalysis only will be summarized by treatment group. The categories for worst case

CONFIDENTIAL

207660

are: No Change/Decreased, Any Increase, Increase to TRA, Increase to 1+, Increase to 2+, Increase to 3+, Increase to 4+. The categorization is determined by comparing the baseline category to the worst case post-baseline category. The determination of the worst case post-baseline takes into account both planned and unscheduled assessments. The percentages are based on the number of subjects in the treatment group with data for the test post-baseline. Subjects with missing baseline value are to be assumed to have normal/within range baseline value.

Shifts from baseline relative to normal range will be summarized by treatment group and visit for Chemistry and Hematology values.

Scatter plot of Chemistry and Hematology at Week 12 versus baseline in Blind Phase will be presented.

The outputs regarding liver events will not be presented unless at least one liver event is observed. See the details in the [Appendix 12](#).

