#### **8.4. Other Safety Analyses**

The analyses of non-laboratory safety test results including ECGs and vital signs will be based on GSK Core Data Standards, unless otherwise specified. The details of the planned displays are presented in [Appendix 12](#): List of Data Displays.

These above data at Screening Visit, in Blind Phase and at Final Visit will be summarized by visit. These analyses will not include the data at QRV, in Open Label Phase and at Early Withdrawal, whereas all the data at all visit will be listed for final analyses.

ECG findings (Normal, Abnormal – not clinically significant, Abnormal -clinically significant) will be summarized by visit.

Values and changes from baseline in ECG and vital sign data will be summarized by visit.

Values and changes from baseline in SpO2 will be summarized and listed by visit. Data at Screening visit, Visit 1 and 5 in Blind Phase and Final Visit will be summarized and those at all visits will be listed including values and changes from baseline.

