Physical examination (simplified version)		X 				X		X 1,t				X		X
Medical history	X	X 												
Vital signs m	X	X 				X		X 1,t				X		X
Height	X													
Body weight	X					X u	X u					X u	X u	
Pulmonary function test	X	X				X	X u					X	X u	X
Electrocardiogram	X					X u	X u					X u	X u	
Pregnancy test n	X	X 				X u	X u					X s, u	X u	X
Laboratory test o	X					X						X		X
Adverse events p	X	X	X	X	X	X	X	X	X	X	X	X	X	X
Concomitant medications/therapies	X	X 	X	X	X	X	X	X	X	X	X	X	X	X
Testing for neutralising antibodies q	X					X								X

- Test items for screening must be performed from 4 weeks to 1 weeks before Day 1 visit (±3 days).
- Eligibility evaluation (Qualification for Retreatment Visit: QRV) will be performed at V5 as a starting point if a participant does not meet the criteria only. The evaluation is performed at a 4-week interval, V5 as a starting point, The QRV when a participant meets the criteria will be a same day as the injection in the next treatment period.
- If a participant is evaluated to meet the eligibility for the injection in the blind phase at V5, the participant will move forward to Part 2 in the open-label phase (Namely, V5 in Part 1 and V1 in Part 2 is a same day). If the participant does not meet the eligibility, QRV will be performed 4 weeks later, at V5 as a starting point.
- If a participant is evaluated to meet the eligibility at V5 in the open-label phase, the participant will move forward to the next treatment phase (V5 and V1 in the next treatment phase is a same day). If the participant does not meet the eligibility, QRV is performed 4 weeks later, V5 as a starting point. If V5 in each treatment phase is at Week 48 after initial injection, V5 will be considered to be completion visit (FV). However, for the testing items, pre-scheduled tests at

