3.50.	Safety 1	LIVER1	Summary of Liver Monitoring/Stopping Event Reporting	This display will be presented if liver events occur.	IA SAC
3.51.	Safety 1	LIVER10	Summary of Hepatobiliary Laboratory Abnormalities	IDSL	IA SAC
ECG					
3.52.	Safety 1	EG1	Summary of ECG Findings	Summarize data at Screening Visit and in Blind Phase. IDSL	IA SAC
3.53.	Safety 1	EG2	Summary of ECG Values	Summarize data at Screening Visit, in Blind Phase and at Final Visit.	IA SAC
3.54.	Safety 1	EG2	Summary of Change from Baseline in ECG Values by Visit	Summarize data in Blind Phase. IDSL	IA SAC
Vital Signs					
3.55.	Safety 1	VS1	Summary of Vital Signs	Summarize data at Screening Visit and in Blind Phase.	IA SAC
3.56.	Safety 1	VS1	Summary of Change from Baseline in Vital Signs	Summarize data in Blind Phase. ICH E3	IA SAC

CONFIDENTIAL

207660

Safety: Tables					
No.	Population	IDSL / Example Shell	Title	Programming Notes	Deliverable
SpO2					
3.57.	Safety 1	SAFE_T2	Summary of Value and Change from Baseline in SpO2		IA SAC
Exposure and Treatment Compliance					
3.58.	Safety 1	SAFE_T3	Summary of Exposure to Study Treatment	ICH E3	IA SAC
3.59.	Safety 1	SAFE_T4	Summary of Extent of Exposure to Study Treatment by Treatment Cycle and Muscle Region	Include total arm in Open label phase only	IA SAC
3.60.	Safety 1	SAFE_T4	Summary of Extent of Exposure to Study Treatment by Treatment Cycle and Joint	Include total arm in Open label phase only	IA SAC

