54.	Safety 1	AE7	Listing of Participant Numbers for Individual Adverse Events	ICH E3	SAC
55.	Safety 1	AE2	Listing of Relationship Between Adverse Event System Organ Classes, Preferred Terms, and Verbatim Text	IDSL	SAC
Serious and Other Significant Adverse Events					
56.	Safety 1	AE8	Listing of Fatal Serious Adverse Events	ICH E3 Including Study Phases for Adverse Events	SAC
57.	Safety 1	AE8	Listing of Non-Fatal Serious Adverse Events	ICH E3 Including Study Phases for Adverse Events	SAC
58.	Safety 1	AE14	Listing of Reasons for Considering as a Serious Adverse Event	ICH E3	SAC

CONFIDENTIAL

207660

ICH: Listings					
No.	Population	IDSL / Example Shell	Title	Programming Notes	Deliverable
59.	Safety 1	AE8	Listing of Adverse Events Leading to Withdrawal from Study	ICH E3 Including Study Phases for Adverse Events	SAC
Hepatobiliary (Liver)					
60.	Safety 1	MH2	Listing of Medical Conditions for Participants with Liver Stopping Events	This display will be presented if liver events occur.	SAC
61.	Safety 1	SU2	Listing of Substance Use for Participants with Liver Stopping Events	This display will be presented if liver events occur.	SAC
All Laboratory					
62.	Safety 1	LB5	Listing of All Laboratory Data for Participants with Any Value Outside Normal Range	ICH E3	SAC
63.	Safety 1	LB14	Listing of Laboratory Data with Character Results	ICH E3 Except for urinalysis data	SAC
64.	Safety 1	UR2A	Listing of Urinalysis Data for Participants	ICH E3	SAC
Other Safety					
65.	Safety 1	EG3	Listing of All ECG values		SAC
66.	Safety 1	EG5	Listing of All ECG Findings		SAC
67.	Safety 1	VS4	Listing of Vital Signs		SAC
SpO2					
68.	Safety 1	VS4	Listing of SpO2		SAC

CONFIDENTIAL

207660

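### Under Section 8.4 the interim for submission holds no vital sign, tabulated or listed, after a second injection; by-visit laboratory tables also omit open-label Week 12 values

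*SAP*

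**What the plan says.** The SAP file holds the April 2018 RAP and its August 2018 amendment. The amendment is current, and the points below are from it unless stated.

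- **Collection.** The schedule in Section 10.2.1 marks vital signs and laboratory tests at V5 (Week 12) of the blind part and of every open-label part, and at the Final Visit. Vital signs are also taken at V1, before injection.
- **Vital-sign and ECG summaries.** Section 8.4 keeps a sentence from Section 7.4 of the April RAP, "These above data at Screening Visit, in Blind Phase and at Final Visit will be summarized by visit", and adds "These analyses will not include the data at QRV, in Open Label Phase and at Early Withdrawal". On listings it says "all the data at all visit will be listed for final analyses".
- **Laboratory summaries.** Section 8.3 says: "These data at Screening Visit, in Blind Phase and at Final Visit will be summarized by visit".
- **Interim displays.** The programming note in Section 10.12.7.1 for Tables 3.41 (chemistry), 3.45 (haematology) and 3.55 (vital signs) is "Summarize data at Screening Visit and in Blind Phase". The matching change tables (3.42, 3.46, 3.56) cover the Blind Phase only. Interim Listings 1-34 include SpO2 (Listing 34) but no vital signs.
- **Final displays.** "Listing of Vital Signs" is Listing 67 in Section 10.12.9.2, for the final deliverable only. Tables 3.133-3.134, 3.119-3.120 and 3.123-3.124 add the Final Visit and no open-label V5.
- **Use of the interim.** Section 3.1 says that it supports regulatory submission.

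**The concern.** Section 2.2 names vital signs and laboratory tests as endpoints for the objective on safety "and tolerability of 400 units of the product". Under Section 2.3 both groups receive 400 units in the open-label phase. The second injection is therefore the 240-unit arm's first exposure to 400 units, and the 400-unit arm's first repeat exposure.

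The V5 measurements in those cycles are the planned objective readings at a fixed interval after such an injection. The plan collects them and then leaves them out of the by-visit summaries. Adverse events, adverse events of special interest, exposure and most efficacy endpoints are all tabulated by treatment cycle, and no reason is given for treating these two endpoints differently. A regulator reading the interim would have no vital-sign measurement with which to judge repeat dosing or the 240-unit arm's move to 400 units.

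**Working it through.** No stated figure in the plan is in dispute. The check traces the data from the schedule to each display.

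**1. Are the data in hand at the interim?** Section 3.1 requires participants re-treated at Week 12 or Week 16 to have completed the open-label Week 12 visit before the cut.
- Re-treated at Week 12: V5 at 12 + 12 = Week 24.
- Re-treated at Week 16: V5 at 16 + 12 = Week 28.
- Re-treated at Week 20: followed to open-label Week 4 (20 + 4 = Week 24), a visit with no vital signs or laboratory tests.

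The first two groups thus have a V5 set. The decision tree in Appendix 14 that fixes each cut-off is not shown in the text, so the Week 16 group rests on Section 3.1 as written.

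**2. Where do those vital signs appear at the interim?** Tables 3.55 and 3.56 stop at the Blind Phase, none of Listings 1-34 shows vital signs, and Listing 67 is final only. Result: nowhere.

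**3. How many participants?** The SAP gives no retreatment rate. If a fraction r is re-treated at Week 12 or 16, 120 × r participants have an omitted interim V5 set.
- Assumed r = 40%: 120 × 0.4 = 48, of whom 60 × 0.4 = 24 are in the 240-unit arm.
- Assumed r = 80%: 120 × 0.8 = 96, of whom 60 × 0.8 = 48 are in the 240-unit arm.

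**4. What does the final analysis tabulate?** Take evaluations every 4 weeks from Week 12 to Week 36, at least 12 weeks between injections, and at most three open-label injections, all at nominal times.
- One open-label injection: 7 paths.
- Two: 4 + 3 + 2 + 1 = 10 paths (second injection at Week 12, 16, 20 or 24).
- Three: 1 path (Weeks 12, 24, 36).
- Total: 7 + 10 + 1 = 18 paths, with 7 × 1 + 10 × 2 + 1 × 3 = 30 open-label V5 visits.

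Under footnote d of the schedule, a V5 at Week 48 counts as the completion visit. That needs a last injection at Week 36, which happens on 6 paths, the same six patterns as in Section 10.3.1. The other 30 − 6 = 24 V5 visits are in no by-visit value or change table. Paths are counted, not participants.

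**5. Can the Final Visit stand in for V5?** For re-treated participants it falls between 48 − 36 = 12 and 48 − 12 = 36 weeks after the last injection. For those never re-treated the gap is 48 weeks. Someone re-treated at Weeks 12 and 24 only has open-label V5 visits at Weeks 24 and 36, neither tabulated, and a Final Visit 24 weeks after the last injection.

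**6. Laboratory data.** The by-visit value and change tables have the same gap. However, the interim worst-case tables (3.44, 3.48, 3.49) and Table 3.51 (hepatobiliary abnormalities) carry no phase restriction. Listing 31 gives all laboratory data for participants with any out-of-range value, and Listing 33 gives urinalysis. The shift tables (3.43, 3.47) have no visit note, so their coverage is unclear. None of these outputs is specified by treatment cycle.

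**The case against.** The best defence is that Section 8.4 makes a deliberate choice: comparative summaries for the controlled phase, listings for the uncontrolled one. It contradicts nothing else in the plan, loses no data and affects no efficacy result or treatment comparison. Open-label safety is also well covered at the interim. Second-treatment tables on Safety 2 present adverse events, intensity, drug-related events, events of special interest, serious events and withdrawals, so a vital-sign or laboratory abnormality reported as an adverse event would be seen. SpO2 is listed.

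Much of this stands, and it rules out several stronger readings that a reader might infer:

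- **That every open-label V5 is lost from the final tables.** A V5 at Week 48 is summarised as the Final Visit.
- **That nothing would show drift with repeat dosing.** The final tables give change from baseline at blind V5 and at the Final Visit, and Listing 67 holds all vital signs. The timing is uneven, but that is not nothing.
- **That open-label laboratory results reach only the worst-case tables.** Table 3.51 and Listings 31 and 33 also take them.
- **That the omission can be sized by an upper confidence limit for an abnormality never observed.** The vital-sign tables report values and changes, and Section 10.8 sets no potential-clinical-importance thresholds. For laboratory data, abnormalities are already counted in tables without a phase restriction.

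The defence does not answer the interim gap. If listings are the chosen vehicle for open-label vital signs, the interim needs one, and it has none. Adverse-event tables capture only what an investigator reports as an event, not the measured values.

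**Conclusion.** The point holds for vital signs at the interim without qualification. The output prepared for submission contains no vital sign, in a table or a listing, after a second injection, although Section 3.1 ensures that such data exist for those re-treated at Week 12 or 16. The number affected is 120 × r, or 48 to 96 participants if r is 40% to 80%; that range is an assumption.

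In the final analysis the gap is partial. Open-label V5 vital signs are tabulated when they fall at Week 48 (6 of 30 visits across the permitted paths, unweighted and at nominal times) and otherwise only listed. For chemistry and haematology the gap is confined to the by-visit value and change tables and is the lesser part of the point.

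This is a shortfall in display, not in collection, and it does not bias any comparison. It is still worth correcting, because these are named endpoints for the safety of 400 units and other outcomes are already shown by cycle.

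**What to change.** 1. In Section 8.4, remove the Open Label Phase from the exclusion as it applies to vital signs.
2. At the interim, add value and change summaries at V5 of the 2nd treatment for vital signs, chemistry and haematology, on Safety 2. In the final analysis, do the same for the 2nd, 3rd and 4th treatments on Safety 2, 3 and 4. Use the 240, 400 and 240 + 400U columns already planned for open-label adverse events, and amend Section 8.3 to match.
3. Produce the vital-sign listing at the interim as well as at the final analysis.
4. State which visits the shift tables cover.

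No new data are needed. The cost is several additional tables, since the existing ones use Safety 1 and cannot simply take extra rows. The new tables describe uncontrolled data and should be labelled as descriptive.
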